8.5 Abnormal Hepatic Function

Drug-induced liver injury is considered if abnormal AST and/or ALT levels are accompanied with abnormal elevation of TBIL, and the following conditions are met without other possible causes. Such cases should always be considered as important medical events.

Table 8 Liver injuries required to be reported as SAEs

Baseline	Normal (AST/ALT and TBIL)	Abnormal (AST/ALT and TBIL)
Treatment Period	ALT or AST $\geq 3 \times$ ULN with TBIL $\geq 2 \times$ ULN and ALP $\leq 2 \times$ ULN and no hemolysis	ALT or AST $\geq 8 \times$ ULN and the increased value of TBIL $\geq 1 \times$ ULN or TBIL $\geq 3 \times$ ULN

Once being notified with the abnormalities, the subject must return to the study site promptly (ideally within 48 h) and receive an assessment. The assessment must include the laboratory tests, detailed medical history, and physical assessment. The possibility of hepatic tumor (primary or secondary) should be considered.

Other than repeated AST and ALT tests, albumin, creatine kinase, TBIL, direct and indirect bilirubin, γ -GT, PT/INR, and ALP should also be tested. Detailed medical history includes history of alcohol, acetaminophen, soft drugs, various supplements, traditional Chinese medicine, chemical drug exposure, family diseases, occupational exposure, sexual behavior, travel, contact with subjects with jaundice, surgery, blood transfusion, hepatic diseases or allergies, cardiac diseases, and immune diseases. Further tests may include the detection of acute hepatitis A, B, C and E, hepatic imaging (such as biliary tract), autoantibodies, and echocardiography. If a retest showed consistency with the criteria outlined in [Table 8](#) and there is no other possible cause, the possibility of drug-induced liver injury should be considered before all the results of etiological tests are accessible. This potential drug-induced liver injury should

be reported as SAEs. Additional dosing with the study drugs should follow the Dose Modification Criteria included in Section [5.2.2](#).

8.6 Management of Drug-Related Toxicities

8.6.1 irAEs

Since the mechanism of sintilimab involves T-cell activation and proliferation, irAEs are likely to be observed during this study. Signs and symptoms of irAEs should be monitored. If there are no alternative causes (e.g. infections), signs and symptoms of the subjects during the study may be related to the immune system.

Refer to Section [5.2](#) for dose adjustments of sintilimab and principles of AE management. Refer to the latest version of NCCN guideline for Management of Immunotherapy-Related Toxicities for a detailed guide on irAE management.

We will continue to collect irAEs until 90th day after the last dose. An irAE should be followed up until it resolves to Grade 0-1 or baseline level, or investigators decide not to follow up anymore with acceptable reasons (e.g. cannot fully recover or getting better).

9 Statistics

9.1 Statistical Analysis Plan

This is a Phase II, open label, single arm study, evaluating the efficacy and safety of sintilimab in subjects with UPS. Up to 25 subjects with UPS will be enrolled.

9.2 Statistical Analysis Population

Intention-to-treat set (ITT): all enrolled subjects who are treated.

Evaluable set (EP): all enrolled subjects who have measurable lesions at baseline and have at least one restaging evaluation. This analysis set is used for ORR analysis.

Safety analysis set (SS): all subjects who received at least one dose of study treatment. The SS is used for all the safety evaluations.

Per-protocol set (PPS): A subset of ITT, refers to subjects who do not have major protocol violations that affect the efficacy evaluation. The PPS is used for the sensitivity analyses of primary efficacy endpoints and key secondary efficacy endpoints.

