Study Objectives	
Primary Objectives:
 
• To evaluate the efficacy of sintilimab in subjects with UPS (ORR at 12W by RECIST 1.1) 
Secondary Objectives:
 
• To evaluate the ORR (RECIST 1.1), disease control rate (DCR), progression-free survival (PFS), overall survival (OS), duration of response (DOR), and safety of sintilimab in subjects with UPS 
Exploratory Objectives:
 
• To evaluate the correlation between biomarkers in tumor tissue and efficacy, including but not restricted to PD-L1 expression level, presence of tertiary lymphoid structures (TLS), transcriptome sequencing, single-cell sequencing, and multicolor immunohistochemistry (IHC) analyses.• To evaluate the correlation between biomarkers in peripheral blood and efficacy, including but not restricted to soluble PD-L1, circulating tumor DNA (ctDNA), identification/quantification of immunologic changes and cytokine analyses

Study Design	
This is a Phase II clinical trial evaluating the efficacy and safety of sintilimab in subjects with UPS.
 
A total of 25 subjects with UPS will be enrolled. Subjects will be treated with sintilimab (200 mg IV on Day 1 Q3W). The treatment will repeat every 3 weeks until progressive disease (PD), intolerable toxicity, initiation of new anti-tumor therapy, withdrawal of consent, lost to follow-up, death, completion of therapy, or any other investigator-determined reasons for treatment discontinuation (whichever occurs first). Treatment will continue for a maximum period of 24 months (starting from the first dose).
 
During the trial, tumor imaging evaluation will be initially performed once Q6W (\pm 7 days) and will be based on RECIST 1.1. After the completion or discontinuation of the study treatment, safety follow-up and survival follow-up will be performed.

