4.4.2 Subject withdrawal

A subject has the right to withdraw from the study at any time for any reasons. A subject must withdraw from the study if the subject or his/her legal representative withdraws informed consent.

A subject can withdraw from the study for the following:

- Screen failures;
- A subject or his/her legal representative withdraws informed consent;
- Death;
- Lost to follow-up;
- Study completion.

A subject who withdraws from the study will no longer receive the treatment and protocol-specified follow-up visits. However, the investigator should make every effort to persuade him / her to complete all the examinations specified for the end-of-treatment visit.

The reasons for withdrawal should be documented in the electronic case report forms (database). A subject who has signed the ICF and received any study interventions cannot be replaced after withdrawal or treatment discontinuation.

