9.3.1.1 Analysis of primary efficacy endpoints

The primary efficacy endpoints is confirmed ORR at 12W, defined as the proportion of subjects with a best overall response (BOR) of confirmed complete response (CR) or confirmed partial response (PR), based on Response Evaluation Criteria in Solid Tumors version 1.1 (RECIST v.1.1) in the evaluable population.

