9.3.1.2 Design and sample size/power

The primary efficacy endpoint will be confirmed ORR at 12W. A patient will be considered as a responder to the treatment if he/she has achieved confirmed complete response (CR) or partial response (PR) determined by RECIST 1.1.

A Simon's two-stage Minimax design will be used to monitor the efficacy of sintilimab. The null hypothesis involves an ORR of 10% that will be tested against an ORR of 30%, i.e. a 20% improvement. In the first stage, 15 patients will be treated. If there is ≤ 1 patient who achieves objective response in these 15 patients, the study will be terminated. If the study moves forward to second stage, an additional 10 patients will be treated leading to a total of 25 patients. Six or more responders out of the 25 treated patients will be considered clinically relevant to justify further investigation. The power of this design is 80% under the 1-sided type I error rate of 5%. The early stopping probability is 55% if the ORR is 10% and the average sample size would be 19.5. Assuming a 5% dropout rate, we will need to enroll up to a total of 27 patients.

Analysis of key and other secondary efficacy endpoints

The key secondary efficacy endpoints are ORR (RECIST 1.1), DCR, DOR, PFS and OS in the evaluable and ITT populations.

The ORR, DCR and corresponding exact 95% CIs of the sintilimab arm will be estimated using binomial distribution.

PFS is the time from first dose to first date of Investigator-determined progression (by imaging),

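### The primary 12-week ORR leaves out treated patients who have no restaging scan, and this set does not match the treated-patient denominator of the Simon rule

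*Combined protocol and SAP*

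**What the plan says.** **Analysis set.** Section 9.2 defines the evaluable set as "all enrolled subjects who have measurable lesions at baseline and have at least one restaging evaluation. This analysis set is used for ORR analysis". Section 9.3.1.1 confirms this for the primary endpoint, which is "based on Response Evaluation Criteria in Solid Tumors version 1.1 (RECIST v.1.1) in the evaluable population". The ITT set in section 9.2 is all enrolled subjects who are treated. It is named for ORR only among the secondary endpoints: "The key secondary efficacy endpoints are ORR (RECIST 1.1), DCR, DOR, PFS and OS in the evaluable and ITT populations". The one sensitivity set named for the primary endpoint is the per-protocol set.

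**Decision rule.** Section 9.3.1.2 counts treated patients at both looks: "In the first stage, 15 patients will be treated", with a stop at one response or none, and then "Six or more responders out of the 25 treated patients will be considered clinically relevant to justify further investigation". Section 3.1 instead speaks of 25 evaluable subjects. Section 9.3.1.3 ties the efficacy and safety reports to the first 15 and then 25 evaluable subjects, and adds that they complete 6 cycles.

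**Enrolment.** The synopsis says "A total of 25 subjects with UPS will be enrolled", and section 9.1 also caps enrolment at 25. Section 9.3.1.2 says "Assuming a 5% dropout rate, we will need to enroll up to a total of 27 patients".

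**The concern.** Being evaluable depends on what happens after treatment starts. The patients removed are those with early death, withdrawal or loss, and none of them can be a confirmed responder. Removing them leaves the numerator unchanged and shrinks the denominator, so any bias in the primary estimate is upward.

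The design's operating characteristics belong to a rule on 15 and 25 patients. The plan describes those patients as treated in one place and evaluable in others, and does not say how the boundaries apply if the two counts differ. In an open-label single-arm trial, the point at which stage 1 is judged and the set behind the reported ORR should not be left to be settled once responses are known.

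**Working it through.** **Inputs from section 9.3.1.2:** null ORR 0.10, target 0.30; stop if 1 or fewer of 15 respond; success if 6 or more of 25; 5% dropout; at most 27 enrolled.

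**Assumption:** q is the share of treated patients with no restaging scan. The documents do not give q. I use 5% (the plan's dropout rate taken as q), with 7% and 10% as further assumptions.

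**1. Reproduce the design.** Early stopping is P(Bin(15,p) ≤ 1). Success is the sum over x = 2 to 15 of P(Bin(15,p) = x) × P(Bin(10,p) ≥ 6 − x).
- At p = 0.10: early stopping 0.549; expected size 15 + 10 × (1 − 0.549) = 19.5; success 0.0328.
- At p = 0.30: success 0.8017; stage 1 stop 0.0353.
- Enrolment: 25/0.95 = 26.3, rounded up to 27.

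The plan's 55%, 19.5, 80% and 27 all reproduce, and the attained type I error is 3.3% against the 5% limit. The arithmetic of the design is sound.

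**2. Shift in the estimate.** The rate among evaluable patients is the all-treated rate divided by (1 − q). A true 10% reads as 0.10/0.95 = 10.5%, 0.10/0.93 = 10.8% or 0.10/0.90 = 11.1%. As an example with two of 25 treated unscanned, six responders give 6/25 = 24.0% (exact 95% CI 9.4 to 45.1%) among treated and 6/23 = 26.1% (10.2 to 48.4%) among evaluable. The decision rule does not use this interval.

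**3. When the decision can change.** For a fixed group of patients the responder count is the same in either set. The decision can differ only if stage 1 waits for 15 evaluable subjects or if more than 25 are treated. The present wording allows both.

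**4. Stage 1 under the null.** Waiting for 15 evaluable can only add responders to those seen in the first 15 treated. The chance that the two counts disagree is therefore the fall in the stopping probability, from P(Bin(15, 0.10) ≤ 1) to P(Bin(15, 0.10/(1 − q)) ≤ 1):
- q = 5%: 54.9% − 52.1% = 2.8%
- q = 7%: 54.9% − 51.0% = 3.9%

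**5. Type I error on the evaluable reading.** Each treated patient responds with probability 0.10, is unscanned with probability q, and is otherwise an evaluable non-responder. Stage 1 is judged at the 15th evaluable subject. Accrual ends at 25 evaluable or 27 treated, and success is 6 or more responders. The ceiling ignores stage 1: P(Bin(27, 0.10) ≥ 6) = 0.0471.

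**6. Power when 25 treated are counted.** If 30% is an all-treated rate, power is the 80.2% in step 1. If 30% is a rate among evaluable patients, the all-treated rate is 0.30 × (1 − q).

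| q | Type I error, evaluable reading | All-treated rate if 30% is among evaluable | Power, 25 treated | Stage 1 stop, 15 treated |
|---|---|---|---|---|
| 5% | 3.9% | 0.285 | 75.4% | 4.6% |
| 7% | 4.1% | 0.279 | 73.3% | 5.0% |
| 10% | 4.4% | 0.270 | 69.9% | 5.8% |

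The fair comparator for 75.4% is the evaluable reading under the same assumption (30% among evaluable, q = 5%, at most 27 treated), which has power 79.4%.

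**7. Enrolment total.** At q = 5%, the chance of having 25 evaluable subjects is 0.95^25 = 27.7% if 25 are treated and P(Bin(27, 0.95) ≥ 25) = 85.0% if 27 are. The choice between 25 and 27 therefore decides whether an evaluable reading of the rule is workable.

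**The case against.** The strongest reply is that the plan does specify the denominator of the primary ORR: sections 9.2 and 9.3.1.1 both name the evaluable set. That stands. A reader might infer that the primary denominator is undefined, and the documents do not support this. The mismatch is between that set and the decision rule.

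Second, few patients may be affected. Eligibility requires measurable disease and an expected survival of at least 12 weeks. Note 12 to the schedule of visits and section 7.1.2 provide for scans after discontinuation for reasons other than radiographic progression. Many who stop early would still be scanned and stay in the set, so 5% is probably an upper guide to q. This also stands. The rule in section 9.3.1.2 that censors subjects without post-baseline imaging provides for such cases but does not show that they are expected.

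Third, some of the wording can be reconciled. Aiming for 25 evaluable and enrolling up to 27 is coherent. Section 4.4.2 says "A subject who has signed the ICF and received any study interventions cannot be replaced after withdrawal or treatment discontinuation", and a reader might take this as a further contradiction, but enrolling extra patients in advance is not replacement. What remains is treated against evaluable, and 25 against 27.

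Fourth, a reader might infer that type I error breaks the 5% limit. With exactly 25 evaluable it would be 5.1% at q = 10%, but that needs about 25/0.90 = 27.8 treated on average, above the cap of 27. Within the cap it cannot pass 4.7%.

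Last, the evaluable reading has more power if 30% is an evaluable rate. That is true, and it is a cost of the change.

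**Conclusion.** The point holds as a modest upward bias in the primary estimate together with a real inconsistency in the decision rule. It should be fixed, mainly for the inconsistency. At q = 5% the inflation is half a percentage point at a true 10%, type I error is 3.9% against 3.3% as designed, and stage 1 decisions differ 2.8% of the time under the null. These sizes rest on q, which the documents do not give, and the type I figures also rest on the cap of 27.

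The planned ITT analysis of ORR softens the problem but does not resolve it. It is a secondary analysis, and the synopsis lists 12-week ORR separately from best ORR, so it may not be the same endpoint. The per-protocol sensitivity analysis does not address unscanned patients.

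A reader might also infer that the main population for PFS and OS should change. Nothing in this point supports that: both are already planned in the evaluable and ITT sets, and the argument here concerns the response denominator only.

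**What to change.** - **Primary set.** In sections 9.2 and 9.3.1.1, analyse 12-week ORR in the ITT set already defined, count patients with no post-baseline scan as non-responders, and keep the evaluable set as a sensitivity analysis.
- **Decision rule.** Apply the existing boundaries to the first 15 and first 25 treated patients, as section 9.3.1.2 words them. No new boundary is needed.
- **Alignment.** Bring the synopsis and sections 3.1, 9.1, 9.2, 9.3.1.1, 9.3.1.2 and 9.3.1.3 to that denominator and to one enrolment total. In section 9.3.1.3, reconcile the 6-cycle condition with the stage 1 and final counts. If 27 is kept, say what the extra two cover, for example patients enrolled but never dosed.
- **Power statement.** Say whether 10% and 30% are rates among all treated patients. If so, the stated 80% stands (exact 80.2%, type I error 3.3%). If 30% is a rate among evaluable patients, restate power as about 75% at q = 5%.

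**Cost.** A protocol and SAP amendment with no extra patients, and a slightly lower reported ORR if anyone is unscanned. Under the evaluable-rate reading, about 4 points of power at q = 5% (79.4% − 75.4%), and a stage 1 stop at the target rate of 4.6% rather than 3.5%.

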9.3 Statistical Analysis Methods

9.3.1 General statistical analysis

Continuous variable data will be summarized using mean, standard deviation, median, maximum, and minimum. Attribute data will be described using frequency and percentage. Student t-test/Wilcoxon test and ANOVA/Kruskal-Wallis test will be used to compare continuous variables between different patient groups. The chi-square test or the Fisher's exact test will be applied to assess the association between two categorical variables.

9.3.1.1 Analysis of primary efficacy endpoints

The primary efficacy endpoints is confirmed ORR at 12W, defined as the proportion of subjects with a best overall response (BOR) of confirmed complete response (CR) or confirmed partial response (PR), based on Response Evaluation Criteria in Solid Tumors version 1.1 (RECIST v.1.1) in the evaluable population.

9.3.1.2 Design and sample size/power

The primary efficacy endpoint will be confirmed ORR at 12W. A patient will be considered as a responder to the treatment if he/she has achieved confirmed complete response (CR) or partial response (PR) determined by RECIST 1.1.

A Simon's two-stage Minimax design will be used to monitor the efficacy of sintilimab. The null hypothesis involves an ORR of 10% that will be tested against an ORR of 30%, i.e. a 20% improvement. In the first stage, 15 patients will be treated. If there is ≤ 1 patient who achieves objective response in these 15 patients, the study will be terminated. If the study moves forward to second stage, an additional 10 patients will be treated leading to a total of 25 patients. Six or more responders out of the 25 treated patients will be considered clinically relevant to justify further investigation. The power of this design is 80% under the 1-sided type I error rate of 5%. The early stopping probability is 55% if the ORR is 10% and the average sample size would be 19.5. Assuming a 5% dropout rate, we will need to enroll up to a total of 27 patients.

Analysis of key and other secondary efficacy endpoints

The key secondary efficacy endpoints are ORR (RECIST 1.1), DCR, DOR, PFS and OS in the evaluable and ITT populations.

The ORR, DCR and corresponding exact 95% CIs of the sintilimab arm will be estimated using binomial distribution.

PFS is the time from first dose to first date of Investigator-determined progression (by imaging),

or to death due to any cause. OS is the time from first dose to death due to any cause. Subjects who neither progress nor die will be censored at the date of their last tumor imaging evaluation. Subjects who do not have any tumor imaging evaluation after baseline will be censored on the date of first dose. The mPFS and mOS and corresponding 95% CI will be estimated via the Kaplan-Meier method, and survival curves will be plotted [13]. Log-rank test will be performed to test the difference in survival between groups [14]. Regression analyses of survival data based on the Cox proportional hazards model [15] will be conducted on PFS or OS. The proportional hazards assumption will be evaluated graphically and analytically, and regression diagnostics (e.g., martingale and Schoenfeld residuals) will be examined to ensure that the models are appropriate. For repeated measures, linear mixed model will be used for continuous outcomes and GEE model will be fit for binary outcomes [16]. Appropriate methods will be applied to analyze correlative data. Other statistical analyses may be performed as appropriate.

DoR: subjects who have achieved CR or PR: from first date of Investigator-determined response to Investigator-determined PD or death; subjects who neither progress nor die: be censored at the date of their last tumor imaging evaluation. The mDoR will be estimated via the Kaplan-Meier method and survival plots will be presented.

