6.2.7 Unscheduled visits

Unscheduled visits may be performed if requested by the subject or investigator. The investigator will carry out relevant examinations based on the subject's status, which includes but is not limited to the vital signs, targeted physical examination, ECOG PS, complete blood count/blood biochemistry/routine urinalysis, and tumor imaging evaluation.

7 Study Evaluation

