7.1.2 Tumor imaging during the study

The imaging method used for the evaluation of tumor burden during each visit should be the same as the one used at baseline. Other affected sites should be examined based on the signs and symptoms of each subject. Baseline evaluation will be conducted within 28 days prior to the first dose of the study treatment, which means the investigator can evaluate the imaging results within 28 days prior to the enrollment.

After the first dose of study treatment, tumor imaging evaluation will initially be performed once Q6W (\pm 7 days) and Q9W (\pm 7 days) starting from Cycle 7, until initiation of a new anti-tumor

therapy, PD (at 12W or after), withdrawal of informed consent, lost to follow-up, death, or completion of the study (whichever comes first).

Patients who have radiographic PD will be allowed to continue therapy if clinically stable till next scheduled scans. If PD is confirmed on the next scan, patient will discontinue therapy. For certain cases which PD cannot be determined, especially on those with equivocal non-target lesions enlargement or equivocal new lesions, the treatment may be continued until signs of clinical instability develop or when PD is confirmed by the investigator in the next scheduled scan. Once PD is confirmed, the disease progression date will be recorded as the date when the suspected PD was initially observed. Definition of clinical stability is as follows:

- Absence of clinically significant signs and symptoms suggesting PD (including worsening laboratory values);
- No reduction in ECOG PS score;
- No rapid PD;
- Absence of rapid progression of disease or progressive tumor at critical anatomical sites (e.g. spinal cord compression) that requires urgent medical interventions.

Tumor evaluations should be performed as scheduled and should not be delayed due to treatment delays, holidays, or any other reasons.

Further tumor evaluations are not required for subjects who discontinue the treatment due to radiographic PD.

For subjects who discontinue the treatment for reasons other than radiographic PD, tumor evaluation should be performed Q12W (\pm 7 days) until one of the followings occurs: start of new anti-tumor therapy, PD, withdrawal of informed consent, or death. A scan at the end of the treatment is not mandatory if it were less than 4 weeks after the last tumor evaluation.

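### PFS and OS are also planned in the evaluable set, which excludes anyone who dies before a restaging scan, so those curves are biased upward; the all-treated set should be the only one

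*Combined protocol and SAP*

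**What the plan says.** Section 9.3.1.2, under the key and other secondary endpoints, names two populations for every endpoint in one sentence: "The key secondary efficacy endpoints are ORR (RECIST 1.1), DCR, DOR, PFS and OS in the evaluable and ITT populations". No order between the two is given.

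Section 9.2 defines them. The evaluable set is "all enrolled subjects who have measurable lesions at baseline and have at least one restaging evaluation", and the next sentence gives its purpose: "This analysis set is used for ORR analysis". The other set has no scan requirement: "Intention-to-treat set (ITT): all enrolled subjects who are treated".

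Both clocks start at treatment. For survival, "OS is the time from first dose to death due to any cause"; PFS likewise runs from first dose, to investigator-determined progression on imaging or death from any cause. Estimation is by ordinary Kaplan-Meier. No landmark, delayed entry or later time origin is mentioned. The same paragraph censors at first dose any subject with no imaging after baseline. It does not say whether that covers subjects who died, or whether it concerns PFS alone.

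Section 7.1.2 schedules imaging every 6 weeks with a 7-day window either side, so the first restaging scan is due between weeks 5 and 7.

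**The concern.** Inclusion criterion 7 already demands a measurable lesion, so what separates the evaluable set from the all-treated set is the restaging scan. A subject earns membership by something that happens after time zero. Someone who dies before being scanned is removed from the OS and PFS risk sets altogether, while those who remain are credited with survival time back to the first dose. This is guarantee-time bias, and leaving these deaths out can only raise the curve.

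The trial has one arm, so its medians have no internal comparator. With two versions of each endpoint and no main one, the choice between them stays open until the data are known.

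This concerns PFS and OS only. The denominator for the response rate is a separate matter, and duration of response is defined only in responders, who have necessarily been scanned.

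**Working it through.** **The plan's own figures.** The plan gives no figure for PFS or OS by analysis set. Its Simon design figures reproduce: with 1 or fewer of 15 stopping the trial and 6 or more of 25 needed at the end, exact binomial calculation gives power 0.802 at a 30% response rate, type I error 0.033 at 10% (within the stated 5%), early stopping probability 0.549 and average sample size 19.51. Enrolment is 25 / 0.95 = 26.3, rounded up to 27. None of these depends on the point below.

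**Inputs**
- First scan at week 6, range 5 to 7 (Section 7.1.2). At 52.18/12 = 4.348 weeks per month, t0 = 1.38 months (1.15 to 1.61).
- Median OS m = 12 to 20 months for advanced soft tissue sarcoma (Section 1.1.1).
- Median PFS 3 months in the expanded pembrolizumab cohort of the same histology (Section 1.1.2).
- Assumption: exponential survival.

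**OS.** The share dying before the scan is 1 − 2^(−t0/m). An exponential has no memory, so the median from first dose among those alive at t0 is m + t0.

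| | m = 12 | m = 20 |
|---|---|---|
| Die before week 6 | 1 − 2^(−1.38/12) = 7.7% | 1 − 2^(−1.38/20) = 4.7% |
| Same, weeks 5 to 7 | 6.4% to 8.9% | 3.9% to 5.4% |
| Expected number of 25 (week 6) | 1.9 | 1.2 |
| Evaluable-set median, months | 13.4 (13.2 to 13.6) | 21.4 (21.2 to 21.6) |
| Relative shift at week 6 | about 11% | 7% |
| 12-month OS, all treated | 50.0% | 66.0% |
| 12-month OS, evaluable | 54.1% | 69.2% |

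**Sensitivity to the early hazard.** Let the hazard before t0 be a fraction f of the later hazard λ, keeping the overall median at m. Then fλt0 + λ(m − t0) = ln 2, so ln 2/λ = m − (1 − f)t0. The median among those alive at t0 is t0 + ln 2/λ = m + f·t0, and the shift is f·t0. With f = 0.5 and m = 12 it is 0.5 × 1.38 = 0.69, about 0.7 months. As f approaches 0 the shift vanishes; if f exceeds 1 it is larger than t0.

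**PFS.** Only deaths before a scan are excluded; progression seen on the first scan still counts. If d is the share dying unscanned, the evaluable-set curve after the scan is S(t)/(1 − d), and its median is 3 × (1 − log2(1 − d)). Taking d from the OS step:
- d = 0.047: median 3.2 months; 12-week PFS 0.529/0.953 = 55.5%.
- d = 0.077: median 3.35 months; 12-week PFS 0.529/0.923 = 57.3%.

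The all-treated values are 3.0 months and 52.9%.

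**Does moving to the all-treated set cure PFS?** Not by itself. If the first-dose censoring rule is applied literally to a subject who dies unscanned, that subject is censored at day 0 and adds nothing to the Kaplan-Meier estimate. The all-treated PFS curve would then coincide with the curve in scanned subjects.

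**The case against.** The best defence is that an analysis without the scan requirement is already planned: PFS and OS in all treated subjects. Section 9.3.5 also calls for PFS and OS of every subject to be presented, so early deaths stay visible. Section 9.2 reserves the evaluable set for response, so the sentence in 9.3.1.2 may be loose drafting rather than an intended second survival analysis. This stands as a reason for modest severity. It does not make an evaluable-set survival curve valid, and on either reading the two sections need reconciling.

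The size is also open to challenge. Entry requires an expected survival of 12 weeks or more and ECOG status 0 or 1, which should reduce early deaths. Against that, Section 1.1.1 says advanced UPS fares worst among the subtypes, so a median taken from sarcoma overall may understate them. Sampling error is far larger than the shift: under the exponential model, even with all 25 deaths observed, a 95% interval around a 12-month median is 12 × exp(±1.96/√25), or 8.1 to 17.8 months. That is fair, but the bias has one direction and is avoidable.

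A reader might infer that no analysed subject can die in the first 6 weeks. The documents do not support that. The scan window opens at week 5, and Section 6.2.7 adds: "Unscheduled visits may be performed if requested by the subject or investigator", with tumour imaging among the possible examinations. A subject stopping early may also have an end-of-treatment scan (Table 1, note 12). Six weeks is the scheduled time, not a guaranteed minimum for each person.

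**Conclusion.** The point holds. As written, Section 9.3.1.2 plans PFS and OS in a set selected on a scan after first dose, with time counted from first dose, and Section 9.2 does not assign the set to that use. The evaluable-set curves are biased upward by construction.

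As an illustration, median OS is about 1.4 months too long (1.15 to 1.6 across the scan window), with 1 to 2 of 25 subjects lost to the set, and a 3-month median PFS reads about 3.2 to 3.4 months. This rests on exponential survival, on a 12 to 20 month median for sarcoma overall, and on a first scan at its scheduled time. The 1.4 months is not an upper limit: it is 1.6 with a week-7 scan, and about 0.7 in the 12-month case if the early hazard is half the later one.

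Two stronger readings are tempting. One is that the trial's conclusion is at risk. It is not: the primary endpoint is response, and the decision rule of 6 or more responders in 25 does not use PFS or OS. The other is that the more favourable curve will be the one reported. The documents leave that choice open but do not show an intention, and they plan no formal comparison with published survival.

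The severity is minor to moderate.

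**What to change.** - In Section 9.3.1.2, separate PFS and OS from the sentence on populations and make the ITT set (all treated) their only analysis set. This agrees with the use that Section 9.2 gives the evaluable set.
- In the paragraph defining PFS and OS, state that a death before any post-baseline scan is an event for both endpoints. State that censoring at first dose applies only to PFS, and only to unscanned subjects who are alive and have not progressed. Without this, the change of set may leave the PFS curve as it was.
- If a curve in scanned subjects is wanted, start it at a week-6 landmark and label it exploratory.

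The cost is a few lines of wording and one analysis fewer. No new data, visits or subjects are needed. The reported figures may be slightly less favourable.
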